4.2 Endpoints

The primary efficacy endpoint for the study is:

- Achievement of an EASI-50 response at Week 16.

The secondary efficacy endpoints for the study will be evaluated at Weeks 4, 8, 12 and 16 (unless otherwise specified) and are:

- Percentage of participants achieving EASI-50 at Weeks 4, 8 and 12.
- Percentage of participants achieving EASI-75.
- Percentage of participants achieving EASI-90.
- Mean absolute change and percentage change from baseline in EASI Score.
- Percentage of participants achieving Validated Investigator's Global Assessment (vIGA) of 0 or 1 with a ≥ 2 -point improvement from baseline.
- Percentage of participants achieving vIGA of 0 or 1.
- Percentage of participants achieving vIGA of 0 at Week 16.
- Mean absolute change and percentage change from baseline in vIGA*BSA (BSA=body surface area).
- Mean absolute change and percentage change from baseline in BSA.
- Percentage of participants achieving BSA-50.
- Percentage of participants achieving BSA-75.
- Percentage of participants achieving BSA reduction to 3% BSA or less.
- Mean absolute change and percentage change from baseline in SCORing Atopic Dermatitis (SCORAD) score.
- Percentage of participants achieving SCORAD-35.
- Percentage of participants achieving SCORAD-50.
- Percentage of participants achieving SCORAD-75.
- Mean absolute change and percentage change from baseline in Dermatology Life Quality Index (DLQI) score.
- Percentage of Participants achieving a reduction of ≥ 4 in the DLQI score, of those with a score of ≥ 4 at baseline at Week 16.
- Mean absolute change from baseline in Peak Pruritus Numerical Rating Scale (PP-NRS) score.
- Percentage of participants achieving a reduction of ≥ 2 in the PP-NRS, of those with a score of ≥ 2 at baseline.
- Percentage of participants achieving a reduction of ≥ 4 in the PP-NRS, of those with a score of ≥ 4 at baseline at Week 16.
- Mean absolute change from baseline in Sleep Disturbance Rating Scale (SD-NRS) score.
- Percentage of participants achieving a reduction of ≥ 2 in SD-NRS score, of those with a score of ≥ 2 at baseline at Week 16.
- Mean absolute change and percentage change from baseline in Patient Oriented Eczema Measure (POEM) score.
- Percentage of participants achieving a reduction of ≥ 4 in the POEM score, of those with a score of ≥ 4 at baseline at Week 16.
- Number of courses of TCS/TCI rescue therapy per participant in Weeks 1-8, 9-16 and for Weeks 1-16.
- Number of days of treatment with TCS/TCI rescue therapy per participant in Weeks 1-4, 5-8, 9-12 and 13-16 and for Weeks 1-16.
- Proportion of participants requiring TCS/TCI rescue therapy in Weeks 1-4, 5-8, 9-12 and 13-16 and for Weeks 1-16.

The secondary safety endpoints for the study are:

- Adverse events and serious adverse events.
- Change from baseline in vital signs.
- Change from baseline in ECG parameters.
- Change from baseline in clinical laboratory parameters.
- Change from baseline in physical examination findings.
- Worst-case change from baseline with respect to potentially clinical important criteria for vital signs, QTcF and clinical laboratory parameters.
- Worst-case change from baseline with respect to values outside the normal ranges for clinical laboratory parameters.

Exploratory endpoints to evaluate the time to onset of clinical response are:

- Time to first achievement of EASI-50.
- Time to first achievement of sustained EASI-50.
- Time to first achievement of EASI-75,
- Time to first achievement of vIGA of 0 or 1 with a 2-point improvement from baseline.
- Time to first achievement of vIGA of 0 or 1.
- Time to first achievement of a ≥ 2 point in improvement in PP-NRS score, in participants with a score of ≥ 2 at baseline.
- Time in days to first sustained ≥ 2 point in improvement in PP-NRS score, in participants with a score of ≥ 2 at baseline.
- Time to first achievement of a ≥ 4 point in improvement in PP-NRS score, in participants with a score of ≥ 4 at baseline.
- Time in days to first sustained ≥ 4 point in improvement in PP-NRS score, in participants with a score of ≥ 4 at baseline.
- Time to first achievement of a ≥ 2 point in improvement in SD-NRS score, in participants with a score of ≥ 2 at baseline.
- Time in days to first sustained ≥ 2 point in improvement in SD-NRS score, in participants with a score of ≥ 2 at baseline.

Exploratory endpoints to evaluate the effect of early use of topical corticosteroid rescue therapy on Week 16 responder status are defined in the following subgroups: the subgroup of participants with no rescue use at any time before Week 16 will be compared to subgroups of participants with rescue therapy use within only the first 4, 8, 12 and 14 weeks of treatment and to participants with rescue therapy use within the 2 weeks and 4 weeks prior to the Week 16 visit. For these subgroups, the following endpoints will be summarized:

- Percentage of participants achieving EASI-50, EASI-75 and EASI-90
- Percentage of participants achieving IGA 0 or 1, with and without a 2-point improvement from baseline
- Percentage of participants achieving BSA-50, and BSA-75

Other exploratory endpoints will be evaluated at Weeks 2, 4, 8, 12 and 16 (unless otherwise specified) and are:

- Percentage of participants achieving vIGA of 0 or 1 with a ≥ 2 Point Improvement from screening.

- Mean absolute change and percentage change from Screening in EASI Score.
- Percentage of participants requiring topical antimicrobial or systemic antibiotic treatment for skin infections by Week 16.
- Changes from baseline in SF-12 Mental Component Score (MCS) and Physical Component Score (PCS) at Weeks 4, 12 and 16.
- Changes from baseline in HADS anxiety and depression scores at Weeks 4, 12 and 16.
- Changes from baseline in ADCT scores at Weeks 4, 12 and 16.
- Daily changes from baseline in the PP-NRS and SD-NRS (Timescale: Days 2 to 140).
- Percentage of participants achieving a reduction of ≥ 2 , ≥ 4 in the PP-NRS, of those with a score of ≥ 2 , ≥ 4 at baseline daily from Day 2 to 112.
- Percentage of participants achieving a reduction of ≥ 2 in SD-NRS score, of those with a score of ≥ 2 at baseline daily from Day 2 to 112.

Note that analyses of the other exploratory endpoints including the following biomarkers exploratory endpoints will be addressed in a separate analysis plan and will not be further discussed in this document:

- Changes from baseline in eosinophils at Weeks 2, 16 and 20.
- Changes from baseline in serum immune protein markers including IgE at Week 16.
- Changes from baseline in immune cell RNA profile at Weeks 2, 16 and 20.

5 Study Methods

5.1 General Study Design and Plan

This is a randomised, double-blind, placebo-controlled study to evaluate the efficacy, safety and tolerability of EDP1815 as compared to placebo in participants with mild, moderate and severe atopic dermatitis.

Cohorts 1, 2 & 3 will be run concurrently, and Cohort 4 recruitment will commence after enrollment for Cohorts 1, 2, & 3 are completed. During the Cohorts 1, 2, & 3 enrolment after eligibility is confirmed during the screening period ([Protocol Sections 5.1 and 5.2](#)), participants will be randomly assigned in a 1:1:1 ratio to 1 of the cohorts 1, 2 or 3. Once recruitment to first three cohorts is completed all participants will enrol cohort 4:

[figure not shown]
- **Cohort 1:** 1.6×10^{11} total cells of EDP1815 or matching placebo administered as 2 capsules once daily.
- **Cohort 2:** 6.4×10^{11} total cells of EDP1815 or matching placebo administered as 2 capsules once daily.
- **Cohort 3:** 6.4×10^{11} total cells of EDP1815 or matching placebo administered as 1 capsule of 3.2×10^{11} cells twice daily.
- **Cohort 4:** 8.0×10^{10} total cells of EDP1815 or matching placebo administered as 1 capsule once daily.

Participants in Cohorts 1, 2, & 3 will be randomised in a 3:1 ratio (approximately 75 to EDP1815 and 25 to placebo within each cohort, 300 in total). Participants in Cohort 4 will be randomised in a 2:1

ratio (approximately 70 to EDP1815: 35 to placebo, 105 in total). So approximately 405 participants will be randomised in total.

As shown in Figure 1, the study comprises a screening period of up to 4 weeks, a treatment period of 16 weeks, and a 4-week post-treatment follow-up period, which results in a maximum study duration of up to 24 weeks. Should a participant elect to participate in an Open Label Extension (OLE) protocol for EDP1815, the follow-up period will be skipped, and the study duration would be a maximum of 20 weeks.

Figure 1 Study Schema

An interim analysis may be undertaken prior to the end of recruitment in cohorts 1-3. The purpose of this interim analysis is to check that the treatment groups have remained balanced and that the use of stratified randomisation has not led to issues caused by multiple incomplete blocks of randomisation. A separate interim analysis process plan is available which provides all relevant details.

5.2 Randomisation and Blinding

Cohorts 1, 2 & 3

At the baseline visit (Visit 2), participants will be randomly allocated, in a 1:1:1 ratio to one of the three cohorts. Within the cohort, participants will then be randomly assigned in a 3:1 allocation ratio to receive either EDP1815 or matching placebo treatment. The randomisation schedule will be stratified by vIGA at Day 1 to ensure that the cohorts and treatment groups within cohort are balanced with respect to disease severity.

Cohort 4

Participants will be randomly assigned in a 2:1 ratio to receive either EDP1815 or matching placebo treatment. The randomisation schedule will also be stratified by vIGA at Day 1. In order to match as closely as possible the severity of Cohorts 1, 2 & 3. Cohort 4 may also limit the numbers of

participants recruited to each strata to match the proportions of each vIGA strata in Cohorts 1, 2 & 3.

Interactive response technology (IRT) will be used for assigning eligible participants to a treatment regimen (cohort and treatment within cohort) based on a predetermined production randomisation and/or packaging schedule.

The allocation to cohort is not blinded, however, treatment allocation within cohort will be fully blinded to participants, study staff and the sponsor with the exception of the personnel supporting the IRT system, the independent randomisation team, the clinical supplies team, the clinical safety team at [REDACTED], and an unblinded team within [REDACTED] who will produce the interim analysis but have no other involvement in the reporting of the study.

A participant's treatment assignment will not be unblinded for the investigator or study site staff until EOS unless medical treatment of the participant depends on knowing the study treatment the participant received. Participants who are unblinded will be allowed to continue their participation in the study; however, the impact of unblinding will be assessed in the supplementary analysis where EDPS5 is used.

Cohorts 1-3 data may be unblinded before the end of the study, after the cohorts 1-3 database lock (DBL) which will occur once all cohorts 1-3 participants have completed 4 weeks of post-treatment follow-up (Week 20 or Early Termination Visit) or entered the OLE study. Cohort 4 data will be unblinded at the end of study.

5.3 Derived variables

5.3.1 General

5.3.1.1 Relative Day and Time

The relative day of an assessment will be calculated as:

- For measurement performed on or after the date of first dose:
Date of assessment – date of start of treatment +1
- For measurements performed before the date of first dose:
Date of assessment – date of start of treatment

5.3.1.2 Baseline

The last non-missing value collected before first study dose will be taken as the baseline measurement for all parameters collected at scheduled visits. If data is collected on Day 1 it will be assumed to be pre-dose regardless of an associated time.

For the daily endpoints baseline will be taken as average of the 7 days before Day 1 (including Day 1 assessment) and will be calculated if there will be at least 4 non-missing values.

5.3.1.3 Change and Percentage Change from Baseline

Change from baseline will be calculated as:

$$\text{change from baseline} = \text{value at timepoint} - \text{baseline value}$$

Change from baseline will be presented to the same level of precision as the original value in the listings.

Percentage change from baseline will be calculated as:

$$\text{percentage change from baseline} = 100 * (\text{change from baseline} / \text{baseline value})$$

Percentage change from baseline will be presented to 1 decimal place (dp) in the listings.

5.3.2 Demographic and Background Data

Height may be recorded in cm or inches. Height in inches will be converted to height in cm as follows:

$$\text{Height (cm)} = \text{Height (inches)} * 0.3937$$

Height (cm) will be presented to 1 dp in the listings.

Weight may be recorded in kg or pounds. Weight in pounds will be converted to weight in kg as follows:

$$\text{Weight (kg)} = \text{Weight (pounds)} * 0.4536$$

Weight (kg) will be presented to 1 dp in the listings.

Body mass index (BMI) will be calculated as:

$$\text{BMI (kg/m}^2\text{)} = \text{Weight (kg)} / [\text{height (cm)} / 100]^2$$

BMI (kg/m²) will be presented to 1 dp in the listings.

BMI will also be categorised as:

- ≥ 30 kg/m²
- < 30 kg/m²

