7.2 Covariates and Subgroups

Subgroups based on baseline severity of disease will be defined as follows:

- Using baseline vIGA score of 3 for efficacy analysis
- Using baseline vIGA score other than 3 for summaries only (2, 4)

For the inferential models defined in [Section 9](#), in addition to the baseline vIGA score and relevant baseline score where applicable, the following covariates will be considered:

- Body mass index (<30 kg/m², ≥30 kg/m²)
- Sex (male, female)
- Race (Non-Hispanic white and Hispanic or Non-White)
- Region (North America, Europe, Asia Pacific)

Covariates selection will be done separately for cohorts 1-3 analyses and cohort 4.

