9.2 Selection of Additional Covariates

For all cohorts 1-3 efficacy analyses, the covariates described in [Section 7.2](#) will be considered and included in the primary efficacy model 1 described in [Section 9.3.3](#) for the primary estimand if found to be significant ($p < 0.05$). A forward stepwise selection method will be used to include the covariates after the baseline vIGA score and baseline EASI score have already been fitted.

The covariates selected for this primary model will also be used in all other analytical models including covariates.

For cohort 4 the process is described in the separate SAP Addendum.

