4.1.1 Selection of Matched Placebo

Selection of matched placebo participants will be made separately by the unblinded team before cohort 4 DBL but close enough to ensure that data needed for analysis is cleaned and will not change for all cohort 4 participants.

Only pre-treatment data (covariates from screening or baseline) of cohorts 1-3 placebo participants and cohort 4 participants and treatment assignments of cohort 4 participants will be provided to the unblinded team for analysis.

The process management details and team responsibilities are described in an interim analysis process plan.

35 placebo participants will be selected from cohorts 1-3. The group will include 5 to 7 participants with mild vIGA score and 3 to 5 participants with severe vIGA score to match cohort 4 vIGA frequencies.

Propensity scores

Propensity scores (PS) will be estimated by a logistic regression model. The treatment assignment (binary: 0 for placebo and 1 for active) is regressed through covariates.

The following covariates will be selected for initial model:

- Categorical: vIGA, sex, region (North America, rest of the world)
- Continuous: BMI, BSA, EASI score

Covariates will come from the last pre-treatment assessment which can be screening, baseline or unscheduled visit. To ensure the fit of the model sex or region may be excluded from covariates list.

Main matching algorithm

Each patient in active treatment group of cohort 4 will be matched with one placebo patient from cohort 1-3 using optimal matching to minimize overall calliper distance of matched pairs (Austin 2011). Initially calliper distance will be set to 0.25 (SD of logit(PS)) and may be increased to get more matches and ensure better balance of covariates.

From all matched pairs, only pairs with loose* vIGA match will be selected.

From the loose matched pairs, 5 pairs with lowest logit(PS) difference where cohort 4 matched subject has mild vIGA score and 3 pairs with lowest logit(PS) difference where cohort 4 matched subject has severe vIGA score will be selected to ensure minimum requested frequency of mild and severe vIGA.

Another 27 pairs will be selected from the remaining loose matched pairs with the least logit(PS) difference to ensure that best matched candidates are chosen.

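### The SAP converts height from inches to centimetres with the inverse factor (0.3937 instead of 2.54), so BMI is about 42 times too high for every participant measured in inches

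*SAP*

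**What the plan says.** SAP 5.3.2 allows two units: "Height may be recorded in cm or inches". It then says "Height in inches will be converted to height in cm as follows", and gives a formula that multiplies the recorded height by 0.3937 to obtain centimetres. It converts pounds to kilograms by multiplying by 0.4536. BMI is then weight in kg divided by the square of height in cm over 100, and is split at 30 kg/m².

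BMI is used in three places:

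- **Covariate selection.** SAP 7.2 lists "Body mass index (<30 kg/m², ≥30 kg/m²" among the candidates. SAP 9.2 selects by forward stepwise entry at p < 0.05 in the primary logistic model, after baseline vIGA and EASI. It adds: "The covariates selected for this primary model will also be used in all other analytical models including covariates". Section 4.2 of the Cohort 4 addendum applies the Cohorts 1-3 selection to the Cohort 4 models as well.
- **Selection of borrowed controls.** Addendum 4.1.1 puts BMI in the initial propensity model ("Continuous: BMI, BSA, EASI score") alongside vIGA, sex and region. The matching picks 35 placebo participants from Cohorts 1-3.
- **Reporting.** SAP 8.3 summarises height and BMI at screening, and both are listed.

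Neither the table of changes in SAP section 13 nor the one in addendum section 6 mentions the conversion.

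**The concern.** One inch is 2.54 cm, so a height in centimetres must be a larger number than the same height in inches. The SAP formula makes it smaller. Because BMI divides by height squared, the error is squared too.

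Two effects follow and should be kept apart. In the efficacy models BMI is a two-level factor, so the 42-fold value does not enter them. What goes wrong is that all participants recorded in inches are put in the ≥30 level whatever their true BMI. In the propensity model BMI is continuous, so the inflated value enters directly, and so do the box plots and standardised differences that judge the match. That matters most for Cohort 4, where half of the planned control group is borrowed and not randomised against the active arm. A small standardised difference in this variable would mainly show balance on the unit of measurement, not on body mass.

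Protocol 9.12.1 measures height at screening only, so no later measurement would serve as a cross-check.

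**Working it through.** **Inputs from SAP 5.3.2:** height factor 0.3937 (multiplied), weight factor 0.4536 (multiplied), BMI = kg/(cm/100)², cut-off 30.

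**Check of the factors.** 1/2.54 = 0.39370, so the height factor is the inverse of the one needed. One pound is 0.45359 kg, so the weight factor is right.

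**Size of the error.** Heights are too small by 2.54/0.3937 = 6.45. BMI is too large by 6.45² = 41.6, independent of height and weight.

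| Participant | Height as written | Height correct | BMI as written | BMI correct |
|---|---|---|---|---|
| 60 in, 100 lb | 23.6 cm | 152.4 cm | 812.9 | 19.5 |
| 68 in, 170 lb | 26.8 cm | 172.7 cm | 1075.9 | 25.8 |
| 76 in, 300 lb | 29.9 cm | 193.0 cm | 1520.0 | 36.5 |

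**Effect on the two-level covariate.** The printed formula classes a participant as ≥30 when true BMI is at least 30/41.62 = 0.72. Every adult recorded in inches meets that. To be classed below 30 at 68 inches, a participant would have to weigh less than 30 × 0.2677² = 2.15 kg.

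**How many are misclassified.** The documents give neither the share of heights in inches (call it f) nor the BMI distribution. Assume true BMI is normal with mean 27 and SD 5.5. Then P(BMI < 30) = Φ(3/5.5) = 0.707, and the misclassified share of all participants is 0.707 f.

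**Effect on the continuous covariate.** With k = 41.62, the variance between the two recording units is f(1−f) × [27(k−1)]², and the variance within them is 5.5² × [f k² + (1−f)]. The share of variance explained by unit is between/(between + within).

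| f | In wrong BMI class | Variance of BMI explained by unit |
|---|---|---|
| 5% | 3.5% | 0.96 |
| 25% | 18% | 0.95 |
| 50% | 35% | 0.92 |
| 75% | 53% | 0.85 |

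The gap between the two unit groups is about 27 × 40.62 = 1,097 kg/m². A true difference of 10 kg/m² between two participants recorded in centimetres is 10/1,097, or about 1% of that gap, so it carries almost no weight in a linear term.

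**A second set of assumptions** (mean 28, SD 6) gives the same picture. At f = 5% the ≥30 proportion moves only from 37% to 40%, but the SD of continuous BMI rises from 6 to about 255. At f = 50% the ≥30 proportion is 69%.

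**The case against.** The formula itself is hard to defend, so the best case on the other side concerns consequence.

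- **Cohorts 1-3 are randomised.** The fixed model contains treatment, vIGA and EASI. BMI enters only if it passes p < 0.05, and a mis-scaled pre-treatment covariate is unrelated to arm except by chance. This stands. The cost there is poorer adjustment and a different conditioning set for the odds ratio, and no bias in the treatment comparison has been shown.
- **The Cohort 4 propensity model has other terms.** vIGA, EASI and BSA are untouched. Region is also in the model and may already capture much of what recording unit captures. The addendum allows covariates to be dropped to reach balance. This partly stands: it has not been shown how far the choice of the 35 controls would change. However, the addendum names sex and region, not BMI, as the terms that may be dropped for model fit.
- **Two sensitivity analyses avoid the matching.** The within-Cohort-4 comparison and the Bayesian analysis do not use the propensity score. That is correct, but the primary Cohort 4 comparison does.
- **Someone would notice.** Adult heights near 27 cm and BMIs near 1,000 would show in the demography summary, the listings and the balance plots. That is likely. The documents do not show whether the code followed the printed factor, and a plan should not depend on programmers departing from it.
- **The inch share is unknown.** Participants recorded in centimetres are unaffected, and the misclassified share could be close to zero. This stands for the two-level covariate. For the continuous term, even a 5% share is enough to swamp true BMI.

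**Conclusion.** The concern holds. The conversion in SAP 5.3.2 is inverted, and following it gives a BMI 41.6 times too high, and a class of ≥30, for every participant recorded in inches. That result is pure unit arithmetic and needs no assumption.

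The number affected does rest on assumptions. With 25-75% of heights in inches and true BMI about normal (27, 5.5), 18-53% of participants are in the wrong class, and recording unit explains about 85-95% of the variance of continuous BMI. SAP 7.2 names North America as a region and SAP 5.3.2 provides for inches, so some inch recording is a realistic case.

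The consequence for the Cohorts 1-3 primary result is conditional on BMI being selected. The more direct exposure is the Cohort 4 propensity score and its balance diagnostics, where BMI is in the initial model without any selection step. This is a fault in the written specification. The documents do not show that any dataset is wrong.

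**What to change.** In SAP 5.3.2, replace the multiplier 0.3937 with 2.54 (dividing by 0.3937 is equivalent). Record the change in the SAP's table of changes.

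Then confirm in the analysis datasets that height, BMI and BMI class for participants recorded in inches come from the corrected factor. Confirm too that the covariate selection, the Cohort 4 propensity scores, the matched set and the balance diagnostics were built on those values. A range check on derived height would catch any recurrence.

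The text correction is one line and involves no design trade-off. If covariate selection or matching has already been run with the printed factor, those steps and the models that depend on them need to be rerun. If the code already used 2.54, only the document changes.
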